### **6.2. Response Evaluable Population**

The Response Evaluable Population is defined as all subjects who receive at least 1 dose of study treatment (KZR-261) and who have a baseline and at least 1 post-baseline anti-tumor response assessment using RECIST v1.1 or PCWG3 in the case of mCRPC. The Response Evaluable Population will be used for the efficacy analyses.

### **6.3. DLT Evaluable Patients**

The DLT Evaluable Population consists of all subjects who either meet the following minimal exposure criteria and have sufficient safety evaluations without having a DLT, or have experienced a DLT during the DLT assessment period.

Subjects who do not experience a DLT in Part 1 Cycle 1 (Dose Escalation) must receive all of their scheduled doses (Days 1, 8, and 15) during the DLT assessment period with completed follow-up data available through 28 days of Cycle 1 to be DLT-assessable.

### **6.4. Pharmacokinetic Analysis Population**

The PK Analysis Population consists of all subjects who receive at least 1 dose of KZR-261 and who have at least one measured post-dose concentration of KZR-261. Any protocol deviations affecting PK analyses may result in exclusion from summaries for individual time point concentrations, complete PK profiles, and/or PK parameters. These exclusions will be reviewed before database lock and confirmed with the Sponsor before implementation. The PK population is more exhaustively detailed in the PK analysis plan.

## **7. GENERAL STATISTICAL CONSIDERATIONS**

### **7.1. Unit of Analysis**

There are several units of analysis in this study. For select efficacy summaries based on the RECIST v1.1 criteria, specifically in the melanoma, mesothelioma, mCRC, and all-tumors cohorts in Part 2A and 2B (Tumor-Specific Dose Expansion and Dose Optimization), the unit of analysis will be the tumor, however, the overall response will be evaluated at the subject level. The tumor is defined as any target, non-target, or new lesions, including metastases, identified

during screening and follow-up imaging. In the case of mCRPC, the study unit will be the subject for efficacy summaries based on the PCWG3 modification of RECIST v1.1 which includes PSA and bone lesion assessments. Slit lamp and visual acuity summaries will be at the eye level. Additionally, AEs, SAEs, clinical laboratory data, physical examination findings, ECG, ECOG PS, biomarker data, and medical history will be presented at the subject level.

## **7.2. Missing or Inconclusive Data Handling**

In general, there will be no imputation of missing data other than for partial or missing dates where complete dates are required to identify data as treatment-emergent or concomitant with treatment. Partial/missing birth dates, start and end dates for AEs and concomitant medications will be imputed such that if the missing part of the date causes ambiguity in the temporal relationship to treatment, it will be assumed to be treatment emergent or concomitant. Specifically, dates will be imputed as follows:

### **7.2.1. Partial/missing start date:**

- Dates with missing day only will be imputed as the 1st of the month unless the month and year are the same as the month and year of first dose of study medication, in which case the missing day will be imputed as the first dose day of study medication.
- Dates with both day and month missing will be imputed as 1 Jan unless the year is same as the year of first dose of study medication, in which case the missing day and month will be imputed as the first dose day and month of study medication.
- Completely missing dates will be imputed as the first dose date of study medication unless the end date is on or before the first dose date of study medication, in which case missing date will be imputed as 1 Jan of the same year as the end date.

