9.1.5. Follow-up of Adverse Events

AEs are intended to be collected according to the procedures outlined above from the time of ICF and are to continue for 30 days following the last dose of study drug.

All Investigators should follow up with subjects with AEs until the event is resolved or until, in the opinion of the Investigator, the event is stabilized or determined to be chronic. Details of AE resolution must be documented in the eCRF.

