### **7.2.2. Partial/missing end date:**

- Dates with missing day only will be imputed as the last day of the month unless the month and year are the same as the month and year of the last dose of study medication, in which case the missing day will be imputed as the last dose day of study medication.
- Dates with both day and month missing will be imputed as 31 Dec unless the year is same as the year of the last dose of study medication, in which case the missing day and month will be imputed as the last dose day and month of study medication.
- If the ongoing flag is missing or “Yes” then the date will not be imputed unless death date is available, in which case the missing date will be imputed as the death date. If ongoing is “No” then the missing end date will be imputed as the last dose date.
- If the imputed date is after the date of death, then the end date will be set equal to the date of death.

The original dates will be displayed in data listings and the imputed dates will be used in derivations only (study day, treatment-emergence status, etc.).

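### SAP 7.2.1: the two partial-start-date rules omit the end-date check, so an adverse event reported as resolved before first dose is flagged treatment-emergent

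*SAP*

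**What the plan says.** SAP 7.2 sets the principle for incomplete dates: "if the missing part of the date causes ambiguity in the temporal relationship to treatment, it will be assumed to be treatment emergent or concomitant".

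SAP 7.2.1 turns this into three start-date rules:

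- Day missing, same month and year as first dose: "in which case the missing day will be imputed as the first dose day of study medication".
- Day and month missing, same year as first dose: "in which case the missing day and month will be imputed as the first dose day and month of study medication".
- Completely missing: the first dose date, "unless the end date is on or before the first dose date of study medication". In that case the start becomes 1 January of the year of the end date.

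For end dates, SAP 7.2.2 sends a missing day in the month of last dose to the last dose day: "in which case the missing day will be imputed as the last dose day of study medication". The rule for a missing day and month is parallel. If the date is wholly missing and the event is marked as not ongoing, "then the missing end date will be imputed as the last dose date". The only limit is death: "If the imputed date is after the date of death, then the end date will be set equal to the date of death". The section closes by saying that listings show original dates and that imputed dates feed derivations, including treatment-emergence status.

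SAP 15.1 defines TEAEs as running from first dose to 30 days after last dose, and keeps events that began before treatment out of the summary tables. Protocol 9.1.5 collects adverse events "from the time of ICF and are to continue for 30 days following the last dose of study drug", so events that start and resolve during screening can be in the database.

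**The concern.** The third start-date rule recognises that an end date can settle the timing. The first two do not use that information. A record with a partial start date is then handled worse than one with no start date at all: the first becomes a TEAE and the second does not.

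The type and incidence of adverse events are primary endpoints in both parts of the study (SAP 2.2.1), and TEAEs are tabulated by dose level in Part 1 (SAP 15.1). Cohorts there are typically 2 to 4 subjects (SAP 4.1.1), so a single misclassified record is visible in a table.

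**Working it through.** The plan states no figure on this point, so the check applies its rules literally. The dates are illustrative.

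**1. Start-date rules.** First dose 15 March; reported end 10 March.

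| Reported start | Rule in SAP 7.2.1 | Imputed start | TEAE? |
|---|---|---|---|
| March, day missing | first | 15 March | yes |
| Year only | second | 15 March | yes |
| Nothing | third, with end-date check | 1 January | no |

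In the first two rows the start falls 15 − 10 = 5 days after the reported end. The event ended before dosing, so it began before dosing. The ambiguity condition of SAP 7.2 is not met, and SAP 15.1 would exclude the event from the tables.

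**2. How often the first two rules apply.** Assume a 365-day year, first dose equally likely on any day, and onset equally likely on each of the 28 days before first dose (the screening window in Protocol 4.1.1). For a lag of j days:

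- Onset is in the month of first dose on 365 − 12j of the 365 possible first-dose days. Summing over j = 1 to 28: 28 × 365 − 12 × 406 = 10,220 − 4,872 = 5,348, and 5,348/10,220 = 52%.
- Onset is in the year of first dose on 365 − j days. The sum is 10,220 − 406 = 9,814, and 9,814/10,220 = 96%.

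These are shares of pre-treatment events that have a partial start date. They are not shares of all adverse events. Only those with a reported end before first dose are misclassified against the SAP's own principle. Such events had time to resolve, so they tend to have started earlier, and the 52% is if anything high for them.

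**3. Effect on a table.** One added subject changes the incidence of a preferred term by 1/n: 1/2 = 50 points, 1/3 = 33 points, 1/4 = 25 points. This is a ceiling. SAP 15.1 counts a preferred term once per subject, so the shift arises only if the subject has no other TEAE with that term.

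**4. Reported or imputed end date in the third rule.** Take a subject who received one dose and has an event marked not ongoing with both dates missing. SAP 7.2.2 sets the end to the last dose date, which is also the first dose date. If that imputed end feeds the third start-date rule, the start becomes 1 January and a possible TEAE is lost, contrary to SAP 7.2. The SAP does not say which end date the rule uses.

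**5. End-date rules.** Last dose 10 July, onset 18 July. An end date reported as July with no day, as year only, or as missing and not ongoing becomes 10 July, 18 − 10 = 8 days before onset. Assume onset uniform over the 30 days after last dose, and a reported end in the month or year of onset:

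- Day missing: (30 × 365 − 12 × 465 + 3)/10,950 = 5,373/10,950 = 49% have an end before onset. The 3 corrects for February having only 28 days.
- Day and month missing: (10,950 − 465)/10,950 = 10,485/10,950 = 96%.

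The event is a TEAE in every one of these cases, because status depends on onset.

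**The case against.** The strongest reply is that moving an uncertain start to Day 1 is a declared conservative convention. That stands wherever the end date does not settle the timing, and the sentence in the first rule is not an error in itself. It does not cover an event with a reported end before first dose, because nothing about its timing is ambiguous.

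A second reply is that SAP 7.2 and 15.1 already point the programmer to the right answer. They do, but SAP 7.2.2 says imputed dates drive treatment-emergence status, so a literal implementation gives the wrong flag. The text has to be reconciled.

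Third, the safeguards are real. Onset and resolution dates are required data (Protocol 9.1.6), missing or inconsistent data are queried (Protocol 11.11), and original dates stay in the listings. Escalation rests on DLTs and Safety Review Committee review (Protocol 3.2.1 and 3.2.1.1), while the SAP analyses follow database lock (SAP 7.4). No dose-escalation decision depends on these imputations.

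A reader might also infer more than the documents support:

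- *That the end-date rules inflate TEAE counts.* They do not. The one case found where an end-date rule touches TEAE status (step 4) removes an event. No duration analysis of adverse events is planned, so no identified table changes.
- *That every post-treatment event with an incomplete end date gets an impossible one.* If the ongoing flag is missing or yes, a missing end date is left alone unless a death date exists. A missing day in a month other than that of last dose goes to month end.
- *That prior medications would be relabelled concomitant.* SAP 10.2 gives no rule that classifies medications by start date alone, so this cannot be shown.

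**Conclusion.** The point holds for the start-date rules. As written, the first two rules of SAP 7.2.1 flag as treatment-emergent an adverse event whose reported end date precedes first dose, against SAP 7.2 and SAP 15.1. This is a stated rule that gives a wrong result.

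The size is small. It needs an event within a screening window of at most 28 days, a partial start date that survived querying, and a reported end before first dose. The documents do not give the number of such records. The 25 to 50 points is the most that one record could do to one preferred term in a cohort of 4 to 2 subjects, and should not be read as an expected bias. The 52% and 96% rest on the uniform-timing assumptions above.

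The end-before-onset dates are a secondary consistency matter with no effect on TEAE counts. The lost TEAE in step 4 depends on the assumption that an imputed end date may feed the third rule.

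**What to change.** In SAP 7.2.1, add to the first two rules: if the reported end date is before first dose, impute the start as the 1st of the month (day missing) or 1 January (day and month missing), and do not flag the event as treatment-emergent. In the worked case the start becomes 1 March or 1 January, and the event is not a TEAE.

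State that all three rules use reported end dates only, never imputed ones. The subject in step 4 then keeps the possible TEAE, and ambiguous records remain treatment-emergent as SAP 7.2 intends. The added check should be strictly before first dose, since an event that ended on Day 1 could also have begun on Day 1.

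In SAP 7.2.2, require that an imputed end date is never earlier than the onset date.

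The cost is a few sentences in the SAP and a small change to the date-derivation code. No data collection changes.

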### **7.2.2. Partial/missing end date:**

- Dates with missing day only will be imputed as the last day of the month unless the month and year are the same as the month and year of the last dose of study medication, in which case the missing day will be imputed as the last dose day of study medication.
- Dates with both day and month missing will be imputed as 31 Dec unless the year is same as the year of the last dose of study medication, in which case the missing day and month will be imputed as the last dose day and month of study medication.
- If the ongoing flag is missing or “Yes” then the date will not be imputed unless death date is available, in which case the missing date will be imputed as the death date. If ongoing is “No” then the missing end date will be imputed as the last dose date.
- If the imputed date is after the date of death, then the end date will be set equal to the date of death.

The original dates will be displayed in data listings and the imputed dates will be used in derivations only (study day, treatment-emergence status, etc.).

### **7.3. Definition of Baseline**

Baseline is defined as the last measurement prior to the dose of KZR-261 on Cycle 1 Day 1. Change from baseline will be calculated as: (Post-baseline Value – Baseline Value).

### **7.4. Data Analysis Conventions**

All data analysis will be performed by [REDACTED] after the study is completed and the database has been locked. Statistical programming and analyses will be performed using SAS® version 9.4 or higher. Output will be provided in rich text format (RTF) for tables and portable document format (PDF) for tables, listings, and figures using landscape orientation. All study data will be listed by subject, dose level in Part 1 (Dose Escalation) and cohort in Part 2A and 2B (Tumor-Specific Dose Expansion and Dose Optimization), and visit (as applicable) based on all enrolled subjects unless otherwise specified. Listings will be sorted by dose level in Part 1 (Dose Escalation) and by cohort in Part 2A (Tumor-Specific Dose Expansion) and Part 2B (Dose Optimization), subject number, visit/time point, and parameter as applicable.

Summaries for continuous and ordinal variables will include the number of observations (n), arithmetic mean, standard deviation, median, minimum, and maximum. Minima and maxima will be reported with the same precision as the raw values; means and medians will be presented to one additional decimal place than reported in the raw values. Standard deviations will be presented to two additional decimal places than reported in the raw values. Summaries for discrete variables will include counts and percentages. All percentages will be rounded to one decimal place (ie, XX.X%). Changes from baseline will be calculated as follow-up visit minus baseline.

Unless otherwise specified, all data will be summarized by dose level and overall, for Part 1 (Dose Escalation), tumor-specific cohort for Part 2A (Dose Expansion), and dose and tumor-specific cohort for Part 2B (Dose Optimization).

### **7.5. Adjustments for Multiplicity**

No multiplicity adjustments will be employed. The secondary efficacy endpoints for which hypothesis testing will be conducted will only occur after an initial pre-defined clinically relevant response has been observed at interim analysis.

## **8. DISPOSITION OF SUBJECTS**

A listing of all enrolled subjects will include the study part (Part 1, Part 2A, Part 2B), the dose cohort in Part 1 (Dose Escalation) or tumor cohort in Part 2A and 2B, the assigned KZR-261 dose, protocol version under which the patient was consented for the trial, enrollment date, and date of informed consent, as well as dates of study treatment discontinuation and study discontinuation (and corresponding study days). For those subjects who discontinued study treatment or the study, the reason for discontinuation will be included.

Subject disposition will be presented in terms of the numbers and percentages for the following: subjects included in Safety, Response Evaluable, DLT Evaluable, and PK Populations, subjects

who discontinued from the study treatment including reason for discontinuation, and subjects who discontinued from the study including reason for discontinuation.

## **9. DEMOGRAPHIC, BASELINE, AND BASELINE DISEASE CHARACTERISTIC VARIABLES**

### **9.1. Demographic and Other Baseline Variables**

The Demographic and other baseline variables including age, age group (<65 years and  $\geq$ 65 years), sex at birth, race, ethnicity, weight, height, body mass index, body surface area, ECOG performance status and childbearing potential, will be summarized for the Safety Population.

Age will be calculated using the following formula:

$$\text{Age} = (\text{Informed Consent Date} - \text{Date of Birth}) / 365.25, \text{ truncated as an integer}$$

A subject listing of these data will also be presented.

### **9.2. Disease Characteristic Variables**

Subject listings that include primary and any secondary cancer diagnoses, tumor measurements, and type (target, non-target) at Screening will be provided.

Baseline disease characteristics, including anatomical location of primary cancer, time since initial-diagnosis, stage at initial diagnosis, stage at study entry, and sites of metastatic disease, will be summarized for the Safety Population. Time since initial diagnosis is calculated as:

$$\text{Time since Initial Diagnosis (days)} = \text{Informed Consent Date} - \text{Initial Diagnosis Date} + 1$$

A subject listing that includes the aforementioned disease characteristics will be provided.

## **10. MEDICAL HISTORY AND CONCOMITANT MEDICATIONS**

### **10.1. Medical History**

Medical history will be coded using MedDRA Version 26.0 or higher. Medical history terms will be listed but not summarized. The listings will also include the onset date, and resolution date (if applicable).

### **10.2. Prior and Concomitant Medications/Therapy**

Prior and concomitant medications/Therapy will be coded using World Health Organization Drug Dictionary (WHODrug) Global, B3, September 2021 or higher and summarized for the Safety Population based on the therapeutic drug class (Anatomical Therapeutic Chemical [ATC] 4 classification) and preferred name. If the ATC 4 classification is not provided, then the next lowest classification that is provided in the coding dictionary will be used.

Prior and concomitant medications/therapy will be summarized separately. Subjects may have more than one medication per ATC classification and per preferred name. A subject will be

counted once within the ATC classification or preferred name if he/she reports one or more medication at each level. Percentages will be based on the number of subjects in each group.

A listing of subjects who received pegfilgrastim or any other bone marrow stimulant will also be provided.

### **10.3. Prior Cancer Therapy Regimen**

A listing of all cancer therapies that includes the treatment or medication name, start date and end date if available, the dose with units, the line of therapy number, and best overall response will be provided.

### **10.4. Prior Radiotherapy**

Prior radiotherapy site, start and end dates, and total dose will be listed.

### **10.5. Prior Cancer-Related Surgery**

A listing of all prior cancer-related surgeries will be provided and include the type, the date and the intent of the surgery (diagnostic or therapeutic).

## **11. DOSING COMPLIANCE AND TREATMENT EXPOSURE**

### **11.1. Dosing Compliance**

All doses of KZR-261 are administered in-clinic, therefore dosing compliance is not expected to be an issue.

### **11.2. Treatment Exposure**

KZR-261 administration will be listed and summarized for the Safety Population in terms of the total number of cycles and doses of KZR-261, cumulative dose administered as well as the number of interruptions and dose reductions. The reasons for dose interruptions and reductions will be summarized.

Cumulative dose will be summarized with continuous descriptive statistics for the Safety Population. A subject listing of cumulative doses of KZR-261 will be generated.

The cumulative dose will be calculated as the sum in mg of KZR-261 administered per subject over the entire course of study. Let  $x$  represent total KZR-261 dose, in mg, administered to a subject at the  $i^{th}$  dosing event out of  $k$  doses administered in cycle  $j$  of  $l$  cycles, then the cumulative dose is given by:

$$\sum_{j=1}^l \sum_{i=1}^k x_{ij}$$

Relative dose intensity will also be listed and summarized. The relative dose intensity will be the cumulative dose divided by the total planned dose, where the planned dose represents the total amount of KZR-261 in mg that would have been delivered to a subject if there were no dose modifications. The planned dose will be included in listings and summaries.

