- Drug-induced liver injury (Hy's law), including all of the following: greater than $3 \times$ ULN elevation in aspartate aminotransferase (AST) and/or alanine aminotransferase (ALT), total bilirubin $>2 \times$ ULN in the absence of findings of cholestasis (ie, absence of alkaline phosphatase elevation to $>2 \times$ ULN) AND no other etiology to explain the combination of increased ALT/AST and total bilirubin.
- FBS >200 mg/dL on 2 consecutive measurements, at least 24 hours apart, over a 7-day period. In the DLT assessment period, subjects who experience FBS >200 mg/dL must have testing repeated within 7 days.

3.2.4. Definition of Maximum Tolerated Dose, Maximum Administered Dose, and Recommended Phase 2 Dose

The estimated MTD is the dose level associated with approximately 30% of DLT-evaluable subjects experiencing a DLT. The target interval for the DLT rate is 25%-35%. Due to the discreteness of the dose levels and in the interest of the safety of subjects, the estimated MTD is the highest tested dose level with a DLT rate $\leq 35\%$ in at least 6-12 DLT-evaluable subjects. In general, the highest dose in Part 1 that provides an acceptable safety profile (MTD or MAD) will also be the highest dose tested in Part 2 unless one or more of the following suggest that an alternate (ie, lower) dose would be preferable:

- Clinically significant anti-tumor effects observed at a lower dose.
- The frequent occurrence of late and relevant AEs that occur after the DLT period.

The MAD is declared without an MTD based on the highest dose level with an observed DLT rate $<25\%$ (the lower bound of the MTD range) and where sufficient safety and efficacy signals have been observed.

The RP2D is the dose chosen for further study based on assessment of a favorable benefit-risk profile across the totality of Phase 1 study results, including both Parts 1 and 2. The RP2D will

take into account late and relevant toxicities that occur after the DLT assessment period in Part 1 and/or the safety/tolerability of multiple cycles of treatment.

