3.6. Planned Duration of Subject Participation (Parts 1, 2A, and 2B)

The study comprises a 4-week Screening Period, a Treatment Period lasting approximately 24 weeks (6 cycles, 4 weeks each), a 30-day Safety Follow-up Period, and a 12-month Long Term Follow-up Period (after last dose of study treatment), for a total study duration of approximately 20 months. Upon completion of Cycle 6, a subject who is deriving clinical benefit may continue treatment at the discretion of the Investigator and with agreement of the Medical Monitor.

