6. DOSAGE AND TREATMENT ADMINISTRATION

6.1. Treatment Administration

For all subjects, KZR-261 will be administered as a 30- to 60-minute IV infusion via a central line on Days 1, 8, and 15 of a 4-week (28-day) treatment cycle. An IV infusion pump or syringe pump will be used for all infusions.

Further details regarding drug product formulation, preparation, and administration of KZR-261 will be provided in a separate Pharmacy Manual.

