6.1.3. Criteria for Initiation of a New Cycle

To commence treatment in Cycle 2 and beyond, subjects must meet the following criteria:

- ANC $\geq 1.25 \times 10^9/L$
- Hemoglobin $\geq 8 \text{ g/dL}$
- PLT count $\geq 75 \times 10^9/L$
- Serum creatinine $\leq 1.5 \times \text{ULN}$ (local institution) or calculated creatinine clearance $>60 \text{ mL/min}$ by the Cockcroft-Gault formula
- Total bilirubin $\leq 1.5 \times \text{ULN}$ (local institution)
- AST and ALT $\leq 3 \times \text{ULN}$ (local institution) or ALT and AST $\leq 5 \times \text{ULN}$ if the subject has hepatic metastases
- FBS $<200 \text{ mg/dL}$
- Serum amylase and lipase values $\leq 1.5 \times \text{ULN}$ (local institution)
- Average QTcF $<470 \text{ msec}$
- Resolution to \leq Grade 2 or baseline of any previously reported Grade 3 or 4 event

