6.1.4. Dose Modification Guidelines for KZR-261

Dose reductions are not permitted during Cycle 1 (DLT assessment period) of Part 1 (Dose Escalation). If a subject experiences an event that qualifies as a DLT, as defined in [Section 3.2.3](#), the subject must be discontinued from study treatment and followed for resolution of AEs as described in [Section 9.1.5](#). Doses may be withheld or reduced for specific AEs and/or laboratory abnormalities in Cycles 2+ for subjects participating in Part 1 and in all cycles for subjects in Part 2 ([Section 6.1.4.2](#)).

Withheld doses should not be made up ([Section 6.1.5](#)).

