6.1.5. Missed Doses

Study treatment should be administered within the visit windows as per the Schedule of Events ([Appendix A](#) and [Appendix B](#)), with an exception for delays in dosing for up to 7 days duration for resolution of toxicity. Missed doses as a result of patient non-compliance will be considered protocol deviations.

Subjects who do not fulfill treatment interruption criteria ([Section 6.1.2](#)) or meet Individual Subject Stopping Rules ([Section 8.1.2](#)) may miss up to 2 consecutive doses or up to 6 doses in total over the first 6 cycles for any reason (eg, AE, scheduling, emergency). Subjects who require more than two dose reductions, or who miss one entire cycle because of an AE(s) must permanently discontinue KZR-261. Missed doses due to implementation of Study Stopping Rules ([Section 8.1.1](#)) should be discussed with the Medical Monitor to evaluate whether KZR-261 should be discontinued.

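### Relative dose intensity in SAP 11.2 has no time term and no defined planned-dose horizon, so toxicity seen only as late cycle starts may not register in it

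*SAP*

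**What the plan says.** SAP 11.2 (Treatment Exposure) gives the definition: "The relative dose intensity will be the cumulative dose divided by the total planned dose". The denominator is described as "the total amount of KZR-261 in mg that would have been delivered to a subject if there were no dose modifications". The section does not say whether that amount runs over the cycles a subject started, over six cycles, or over calendar time on treatment. It also does not say whether a late cycle start is a dose modification. The other exposure outputs are numbers of cycles and doses, cumulative dose, and numbers of interruptions and reductions with their reasons. Treatment duration and the number or length of cycle delays are not listed.

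The schedule and the rules that produce delays are in the protocol:

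- Section 6.1 places doses on "Days 1, 8, and 15 of a 4-week (28-day) treatment cycle". Section 3.6 describes "a Treatment Period lasting approximately 24 weeks (6 cycles, 4 weeks each" and allows treatment to continue beyond Cycle 6.
- Section 6.1.3: "To commence treatment in Cycle 2 and beyond, subjects must meet the following criteria"; a list of laboratory and adverse-event recovery conditions follows.
- Section 6.1.5 holds dosing to the visit windows, "with an exception for delays in dosing for up to 7 days duration for resolution of toxicity".
- Section 6.1.4: "Withheld doses should not be made up".
- Section 3.2.4 has the RP2D take account of late toxicities and/or "the safety/tolerability of multiple cycles of treatment".
- Section 3.4 randomizes about 30 subjects per tumor type 1:1 between the MTD/MAD and a lower dose in Part 2B.

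**The concern.** Dose intensity is ordinarily dose per unit time. The SAP uses the name for a ratio of two amounts. In this trial delay is a built-in response to toxicity: every cycle from the second waits on recovery criteria. Some entries in Protocol Tables 3, 4 and 7 also withhold treatment until recovery without requiring a reduction, for example slow-resolving Grade 3 thrombocytopenia and a first episode of febrile neutropenia. A cycle that starts late but is then given in full loses no mg.

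The open denominator is a second, separate problem. Two programmers working from SAP 11.2 could report different figures from the same dosing records.

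What is at stake is one measure of how well each dose can be sustained over repeated cycles. It matters most in Part 2B, where about 15 subjects per dose and tumor type inform the RP2D. Exposure falls under the SAP 7.4 default, which is by dose and tumor cohort in Part 2B, whereas SAP 15.1 specifies adverse-event summaries by tumor cohort for Parts 2A and 2B. Relative dose intensity is therefore one of the tolerability measures that would be shown by randomized dose.

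**Working it through.** The documents give no value or threshold for relative dose intensity, so there is no stated figure to reproduce. The schedule is internally consistent: 6 cycles × 28 days = 168 days = 24 weeks, and 6 × 3 = 18 doses, in agreement with Protocol 3.6.

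**Inputs.** Three doses per 28-day cycle (Protocol 6.1); six cycles (3.6); 7 days, the only length the documents give for a permitted delay (6.1.5). *Assumptions:* the same delay before each of Cycles 2 to 6, all 18 doses given in full, constant mg per dose. The 3- and 14-day rows are also assumptions, to show the range; 14 days exceeds what the documents state.

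**Formulas.**

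- SAP ratio, planned dose over cycles started or as 18 doses: doses given / 18.
- SAP ratio, calendar reading: doses given / doses an undelayed schedule would have reached by the day of the last actual dose.
- Time-based: (dose given / actual weeks) / (dose planned / planned weeks). With all 18 doses given this is 24 / actual weeks, where actual days = 168 + 5 × delay.

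| Delay before each of Cycles 2–6 | Actual weeks | SAP ratio, cycles started or 18 doses | SAP ratio, calendar reading | Time-based |
|---|---|---|---|---|
| 0 days | 168/7 = 24 | 18/18 = 100% | 18/18 = 100% | 100% |
| 3 days | 183/7 = 26.1 | 100% | 18/19 = 94.7% | 168/183 = 91.8% |
| 7 days | 203/7 = 29 | 100% | 18/21 = 85.7% | 24/29 = 82.8% |
| 14 days | 238/7 = 34 | 100% | 18/25 = 72.0% | 24/34 = 70.6% |

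For the calendar reading with 7-day delays, the last dose falls on day 5 × 35 + 15 = 190. An undelayed schedule continued past Cycle 6 would have reached 21 doses by then, the last on day 183.

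**Shorter treatment.** Two full cycles with one 7-day delay between them give 56/63 = 88.9% on a time basis, so the gap is smaller for subjects who stop early.

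**Effect of the horizon alone.** Two full cycles and then progression: 6/6 = 100% over cycles started, 6/18 = 33% over six cycles. Eight full cycles against 18 planned doses: 24/18 = 133%.

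**What the SAP ratio does register.** Withheld doses are not made up. One lost dose in 18 gives 17/18 = 94.4%; six, the most that Protocol 6.1.5 allows over the first six cycles, give 12/18 = 66.7%. Reductions lower it too.

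**The case against.** A reader might infer that delays can never lower the SAP figure, and that a poorly tolerated dose would pass unseen at 100%. The documents do not support that:

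- The horizon is undefined, and on a calendar reading delays do register (85.7% in the 7-day example).
- A score of 100% needs toxicity that appears only as delay. Withheld doses are lost. Protocol Tables 2, 3, 4 and 7 require reduction for several toxicities, and Table 5 stops treatment for Grade 3 or higher amylase or lipase.
- Interruptions and their reasons are summarized under SAP 11.2, and the overall summary in SAP 15.1 includes adverse events leading to interruption.
- In Part 1, an adverse event that delays Cycle 2 by more than 7 days is itself a DLT (Protocol 3.2.3).

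Three further inferences also go too far. Delay is not shown to be the main tolerability signal: the primary safety endpoints are DLTs (Part 1), adverse events, deaths, reductions, interruptions and discontinuations, and the like. Nor is the ratio shown to favor the higher dose, since that needs delays to concentrate there and the documents give no such figure. And dividing one cycle by itself plus its delay (28/35 = 80%, 28/42 = 67%) overstates the loss, because six cycles contain five gaps.

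Finally, no decision rule uses relative dose intensity; the RP2D rests on the totality of results.

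All of this stands and limits the point. It does not remove it. That a calendar reading would capture delay shows that the definition needs a choice, which the SAP does not make. The interruption counts carry no duration, and it is not stated whether a late cycle start is an interruption.

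**Conclusion.** The point holds in a limited form. The ratio in SAP 11.2 carries a name it does not fit, because it has no time term, and its denominator has no stated horizon. If planned dose is counted per cycle started or as 18 doses, delay-only toxicity is invisible in it: 100% against 82.8% for 7-day delays before Cycles 2 to 6, or 70.6% if delays of 14 days occurred. The choice of horizon alone moves a subject who stops after two full cycles between 100% and 33%.

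The delay figures assume uniform delays and full delivery of all 18 doses, so they illustrate size and do not predict the trial's result. This is a defect in one descriptive exposure measure. It is worth correcting before analysis because that measure bears on comparing the Part 2B doses over several cycles.

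**What to change.** In SAP 11.2:

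1. **Define relative dose intensity with time in it.** RDI = (cumulative mg/m² given / W) / (planned mg/m² per week). W is the actual number of weeks from first dose to the planned end of the last cycle started, delays included. Planned mg/m² per week = [sum over cycles started of 3 × assigned mg/m²] / (4 × number of cycles started). The assigned dose is the enrolled or randomized level. It changes only for an approved intra-subject escalation in Part 1, so that escalated subjects do not exceed 100% for that reason. Toxicity reductions leave it unchanged and therefore still lower the ratio. In the 7-day example at a constant dose D this gives (18D/29) / (18D/24) = 82.8%.
2. **Rename the present ratio** *percent of planned dose received*, with planned dose limited to cycles started.
3. **Summarize both**, with treatment duration and the number and days of cycle delays, by dose level (by dose and tumor cohort in Part 2B). State whether a late cycle start counts as an interruption.

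The cost is SAP wording and one extra derivation from dosing dates already collected, with no new procedures or subjects. The reported figure will be slightly less favorable. Under both measures, doses not given in a cycle that is cut short count against the subject whatever the reason for stopping, so the table should carry a footnote saying so.
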